three times within the COS by POEM, RECAP and in the three variations of DLQI. The questions about patient's itch intensity are asked twice in the HOME COS by RECAP and the NRS itch questionnaire. While some repetition can be useful to ensure the consistency of responses, excessive repetitions of a question can reduce the accuracy of the data collected due to the burden on participants. There needs to be a balance between collecting the necessary data to analyse and respecting the participant's time and effort. Based on the results, recommendations will be made to HOME on how to best collect data about patient-reported itch.

Filling Validation Gaps

This project will explore whether all itch questions are required to be included in the HOME COS. This will be the first step to inform future HOME consensus discussions on this topic. If avoidable redundancy is identified, this could help the uptake of the COS by minimising the burden of data collection when using the HOME COS (Williams et al., 2022).

This will be done by exploring the relationship between the responses of the itch questions from different questionnaires, using various statistical methods. This project is a secondary data analysis project using the Eczema Monitoring Online (EMO) trial dataset. The EMO dataset includes data from the RECAP, POEM, and NRS-11 questionnaires. Since the EMO trial did not assess the quality of life the itch questions from the quality-of-life instruments will not be assessed in this project.

Methods

Aim:

To explore the relationship between the different itch questions contained in the HOME core outcome set and understand the implications for implementation of the core set.

Research question 1:

Are the identical questions included in the POEM and RECAP questionnaires (frequency of itch) sufficiently similar to enable collection only once?

Research question 2:

Is there redundancy in the HOME core outcome set itch questions or do they all add value?

Study design

This will be a secondary data analysis project using existing data collected in a previously conducted online trial (EMO). Ethical approval for the EMO trial was obtained from the University of Nottingham Research Ethics Committee (reference number: 239-0421). This study does not require ethical approval because it uses the already existing EMO dataset for secondary analysis.

Data sources

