Eczema Monitoring Online (EMO) trial dataset is accessible from https://rdmc.nottingham.ac.uk/handle/internal/10456. The dataset contains patient-reported outcome assessments collected at baseline and week 8, assessed by the EMO trial dataset includes a

total of four itch questions from POEM, RECAP and NRS Itch as shown in Table 1. The DLQI is not part of the database so it will not be included.

Table 1. Itch questions available in the EMO trial dataset

Questionnaire	Question	Frequency or Intensity
RECAP	Over the last week, on how many days has your skin been itchy because of your eczema?	Frequency
POEM	Over the last week, on how many days has your skin been itchy because of the eczema?	Frequency
RECAP	Over the last week, on how many days has your skin been intensely itchy because of your eczema?	Intensity
NRS Itch	On a scale of 0 to 10, with 0 being 'no itch' and 10 being 'worst itch imaginable', how would you rate your itch at the worst moment during the previous 24 hours?	Intensity

The kappa and correlation will only use the data from baseline (not week 8 after the intervention) The main variables that will be investigated from the database are the POEM frequency of itch, RECAP frequency of itch, RECAP intensity of itch, NRS intensity of itch questions. The variables used will also include all questions from baseline and follow-up in POEM and all baseline questions in RECAP (see Appendix).

Statistical analysis and sample size

Analysis methods

This is an exploratory secondary project and is not formally testing a hypothesis. Analyses will use STATA (version 18) and will focus on descriptive statistics. Statistics will be presented with 95% confidence intervals (CI) where appropriate.

Objective 1: To assess the level of agreement between the POEM and RECAP 'frequency of itch' questions

Levels of agreement between the identically worded frequency of itch questions in the POEM and RECAP will be evaluated using both a weighted kappa (primary method) and kappa.

The itch question is an ordinal scale from 0 to 4 (ranging from no days to every day). Kappa weightings will be applied using a quadratic approach as follows (Sim and Wright, 2005):

- Difference of 0 between the POEM and RECAP questions = 1.00
- Difference of 1 between the POEM and RECAP questions = 0.89
- Difference of 2 between the POEM and RECAP questions = 0.56
- Difference of 3+ between the POEM and RECAP questions = 0.00

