A high level of agreement (suggesting that the item may not need to be asked twice) is defined as being a correlation \geq 0.8.

Objective 2: To explore the impact of using the 'first collected answer' to the frequency of itch question on the EMO trial results.

For the analysis exploring impact on the EMO trial results, the original syntax from the trial analysis will be used. The trial results will be re-calculated using the total POEM scores at baseline and week 8, which have been calculated in two ways:

- Using the original POEM scores (7-items, range from 0 to 28)
- Using 6 items from the original POEM score, plus the frequency of itch question from the RECAP outcome instrument (7 items, range 0 to 28)

Trial results will be presented with mean between group difference and 95% CIs to explore the likely impact on the trial conclusions of collecting the frequency of itch questions only once.

Objective 3: To assess the correlation between all available itch measurements:

The association between frequency of itch questions (POEM and RECAP) and intensity of itch questions (RECAP and NRS-itch) will be explored using Pearson's correlation coefficients and 95% confidence intervals.

A high level of agreement (suggesting that the item may not need to be asked twice) is defined as being a correlation \geq 0.8.

Results of this project will help provide the evidence for HOME to resolve any uncertainties in the assessment of itch in the current COS. In turn, this will improve the accuracy and feasibility of the HOME COS and help to enhance its uptake.

Sample size

The sample size was determined by the availability of required data in the EMO trial.

Consensus-based Standards for the selection of health Measurement Instruments (COSMIN) helps researchers evaluate the psychometric properties of outcome measurement instruments. For studies assessing construct validity, COSMIN recommends that a sample size of over 100 is appropriate to use (Prinsen et al., 2016); the EMO trial has a sample size of >200. Only data from self-completers will be used, data from parents of children will be excluded due to the low number of participants (n = 15).

Patient and Public Involvement

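### Research question 2 asks whether every itch item adds value, but for the four items jointly, and for any pair with an intensity item, the only planned analysis is pairwise Pearson correlation, which cannot show joint redundancy

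*Protocol*

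**What the plan says.** The Methods section of the protocol poses research question 2 as "Is there redundancy in the HOME core outcome set itch questions or do they all add value". The objective that spans all four items is Objective 3, under Statistical analysis and sample size: "To assess the correlation between all available itch measurements". Its method is that the associations "will be explored using Pearson's correlation coefficients and 95% confidence intervals". The criterion for strong agreement follows: "suggesting that the item may not need to be asked twice) is defined as being a correlation" of at least 0.8. The same sentence also stands under Objective 1; the point here concerns its use under Objective 3.

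The Data sources section limits the data: "The kappa and correlation will only use the data from baseline (not week 8 after the intervention").

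Objective 1 (weighted kappa and kappa) and Objective 2 (re-running the trial result with the RECAP frequency item in place of the POEM one) deal only with the POEM/RECAP frequency pair.

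Table 1 labels two items as intensity. The RECAP item asks "on how many days has your skin been intensely itchy because of your eczema", over a week. The NRS item asks "how would you rate your itch at the worst moment during the previous 24 hours", on a 0 to 10 scale.

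**The concern.** An item adds value if it carries information that the other collected items do not. A pairwise correlation takes one partner at a time and ignores the rest. It leaves two things open: what the unshared part of an item contains when r reaches 0.8, and how much of an item the other three already cover jointly.

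This matters most for the intensity items. They have no kappa and no trial re-analysis to fall back on, and the two differ in content, scale and recall period.

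The protocol says under Itch Questions in HOME COS, and again under Publication and dissemination, that the results will feed recommendations to HOME. A pre-specified cut-off is likely to be quoted there as the answer to research question 2, although it does not measure what that question asks.

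**Working it through.** The protocol reports no correlations and gives no derivation for 0.8, so there is no figure to reproduce. The documents supply the cut-off (0.8), the number of items (4), the trial size (296) and the excluded parent-completed records (15). All other inputs below are assumed for illustration.

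**1. Variance left unshared at the cut-off.** Unshared share = 1 − r².
- r = 0.80: 1 − 0.64 = 0.36, or 36%.
- r = 0.85: 1 − 0.7225 = 0.2775, or about 28%.

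**2. Precision at the cut-off.** If the 15 belong to the 296 (an assumption), n = 296 − 15 = 281. The Fisher-z 95% interval for an observed r = 0.80 is tanh(atanh(0.80) ± 1.96/√278), which is 0.754 to 0.839. The unshared share then runs from 1 − 0.839² = 0.30 to 1 − 0.754² = 0.43.

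**3. Reaching 0.8 does not show that an item adds nothing.** Let two items correlate at r, and let them correlate at a and b with some outside rating. With both items in the model, R² = (a² + b² − 2abr)/(1 − r²). Assume r = 0.80, a = 0.50, b = 0.70.
- First item alone: 0.50² = 0.25.
- Both items: (0.25 + 0.49 − 0.56)/0.36 = 0.18/0.36 = 0.50.

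The second item doubles the explained variance, although the pair reaches the cut-off.

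**4. Pairwise r does not show joint predictability.** If all six correlations among four items equal r, the R² of any item on the other three is 3r²/(1 + 2r). Assume r = 0.75.
- R² = 3 × 0.5625/2.5 = 0.675, so multiple R = 0.82.
- The best single partner gives 0.75² = 0.5625.

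The other three together explain 0.675 − 0.5625 = 0.1125 more than any one of them, and the planned table would not show it. This item is still not redundant, since 1 − 0.675 = 32.5% is unshared.

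A limiting case makes the point more sharply. Take an item equal to (x₁ + x₂)/√2, with x₁ and x₂ uncorrelated and of unit variance. It has r = 1/√2 = 0.71 with each of them, and R² = 1.00 on the two together. It is fully determined by the others, yet no pair involving it reaches 0.8.

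**The case against.** The other side has several good points.

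- **No converse rule.** A reader might infer that an item with r below 0.8 is to be kept as adding value, so that the rule errs in both directions. The protocol does not say this; it attaches a meaning only to values of at least 0.8. One can build a case with r = 0.60, a = 0.70, b = 0.42, where R² = (0.49 + 0.1764 − 0.3528)/0.64 = 0.49, the same as 0.70² for the first item alone. That warns against reading a low r as added value, but it does not show a stated rule failing.
- **Hedged wording and exploratory status.** The criterion only suggests that a repeat might be dispensable. The study tests no hypothesis, and it describes itself as a first step towards consensus discussions. This lowers the stakes.
- **Other analyses exist.** Objectives are not formally assigned to research questions, and the frequency pair also has kappa and the trial re-analysis. It would be too strong to call Pearson r the only analysis bearing on research question 2. The description holds for the four items jointly and for every pair with an intensity item.
- **A pairwise view fits the burden question.** The instruments were validated separately, so items cannot simply be dropped, and asking whether a repeat is needed is a pairwise matter. That is a fair reason to keep the correlations. It does not make them an answer to whether all the items add value.
- **R² on the other items is also shared variance.** This is true: it does not measure value either. It does measure joint overlap, which pairwise r cannot, and reporting 1 − R² beside it states openly what is left.

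Nor is this detail left for an analysis plan, because the protocol itself fixes both the method and the cut-off.

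**Conclusion.** The point holds in a limited form. Objective 3 measures less than research question 2 asks, for the four items together and for every pair with an intensity item. At the cut-off, 36% of the variance is unshared (about 30% to 43% over the 95% interval if n = 281), and predictability from the other three items jointly is not examined.

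The 36% follows directly from the protocol's own threshold. The examples in steps 3 and 4 rest on assumed correlations and show what can happen, not what does happen in EMO. A reader might conclude that the project will misclassify particular items; the documents contain no data to support that. This is a worthwhile, inexpensive improvement and does not invalidate the planned work.

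**What to change.** In Objective 3:

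1. Keep the matrix of Pearson correlations with 95% confidence intervals, as description.
2. At baseline, in self-completers, regress each of the four itch items (poem_a_10, recap_a_20, recap_a_30, nrs_itch0) on the other three. Report R² and the unshared share 1 − R², each with a bootstrap 95% confidence interval. Linear regression scores the ordinal frequency items as numbers, as Pearson's coefficient already does, so it brings in no new scaling assumption.
3. Word the conclusions on research question 2 as information shared and not shared with the other items, and do not declare redundancy from r of at least 0.8 alone.
4. Optionally, show the gain in R² for recap_a_10, or for the sum of the six non-itch POEM items, when itch items are added. Label this an exploratory sensitivity analysis, and note that each anchor comes from the same questionnaire as some of the itch items and may favour them. It should not be the basis for answering research question 2.

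All the variables are already in the Appendix codebook. The cost is four regressions with bootstrap intervals and conclusions that are less clear-cut than a pass or fail at 0.8.

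### Objective 2 gives each POEM version its own 95% CI but no interval for the change in treatment effect that the item swap causes

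*Protocol*

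**What the plan says.** The Objective 2 paragraph under Analysis methods states that "the original syntax from the trial analysis will be used" and that "The trial results will be re-calculated using the total POEM scores at baseline and week 8, which have been calculated in two ways". One version is the standard seven-item POEM, scored 0 to 28. The other is built by "Using 6 items from the original POEM score, plus the frequency of itch question from the RECAP outcome instrument", also scored 0 to 28. The output is fixed as follows: "Trial results will be presented with mean between group difference and 95% CIs to explore the likely impact on the trial conclusions" of asking the itch-frequency question only once.

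The same section sets the general framework: "This is an exploratory secondary project and is not formally testing a hypothesis", and "Statistics will be presented with 95% confidence intervals (CI) where appropriate". Objectives 1 and 3 each have a cut-off of 0.8. Objective 2 has no cut-off, no planned difference between the two estimates and no interval for that difference. It also has no rule based on overlapping intervals or on significance.

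**The concern.** The impact of the swap on the trial result is the modified treatment effect minus the original one. The two effects are estimated on the same people from nearly the same score, so they are strongly correlated. The width of each separate interval describes uncertainty about the treatment effect on the whole POEM score, not about the change. A reader shown two similar intervals could take their overlap as reassurance that it does not provide.

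This matters because Objective 2 is the only analysis that uses post-intervention data: the Data sources section limits kappa and correlation to baseline. It is thus the only place where the two itch items could be seen to diverge by arm. The codebook in the Appendix shows that the intervention arm completed POEM weekly for 8 weeks and the control arm only at baseline and week 8. A difference between arms in how the two items are answered is therefore conceivable, though nothing in the protocol shows that it occurs. The results are to go to HOME to inform its recommendations.

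**Working it through.** **Stated figures.** The protocol gives no SD, power or effect size for Objective 2, so there is no calculated figure to reproduce. The score range checks: 7 items × 4 = 28.

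**What cancels.** For each participant:

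modified total − original total = (six shared items + RECAP itch) − (six shared items + POEM itch) = RECAP itch − POEM itch.

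Each item runs from 0 to 4, so a person's total moves by at most 4 of 28 points. For unadjusted week-8 means, the change in treatment effect is exactly the between-arm difference in mean (RECAP itch − POEM itch). With baseline adjustment it is close to this but not identical, because the baseline score changes too. The EMO model is not described in the protocol.

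**Inputs.**
- N: the synopsis gives 296. The Sample size section gives more than 200 and excludes 15 parent-completed records, so 296 − 15 = 281 if the 296 includes them. Week-8 completeness is not stated; I use 200 to 281.
- Assumed, not in the documents: 1:1 allocation, total SD 5 to 7, item SD s = 1.0 to 1.3, item correlation r = 0.8 or 0.5.

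**Each separate CI.** Half-width = 1.96 × SD × √(4/N).
- Smallest: 1.96 × 5 × √(4/281) = 1.17.
- Largest: 1.96 × 7 × √(4/200) = 1.94.

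**Paired contrast.** Half-width = 1.96 × s × √(2(1 − r)) × √(4/N).
- r = 0.8: 1.96 × 1.0 × 0.632 × √(4/281) = 0.15, to 1.96 × 1.3 × 0.632 × √(4/200) = 0.23.
- r = 0.5: 1.96 × 1.0 × 1 × √(4/281) = 0.23, to 1.96 × 1.3 × 1 × √(4/200) = 0.36.

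**Ratio at equal N** = SD / (s√(2(1 − r))).
- r = 0.8: 5/0.822 = 6.1 to 7/0.632 = 11.1.
- r = 0.5: 5/1.3 = 3.8 to 7/1.0 = 7.0.

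These widths are unadjusted. Baseline adjustment narrows the separate intervals and reduces the ratio. In a simulation with a baseline-adjusted model, N = 280, total SD about 6.3 and item correlation about 0.8, the half-widths were 1.27 and 0.18, a ratio of about 7.

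**How the planned display behaves under different readings.** The simulation used 1,500 trials per scenario, N = 200 and 280, and total SD about 6.0 to 6.4.

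| Reading | No true shift between arms | Shift about 0.57 points | Shift about 1.1 points |
|---|---|---|---|
| Separate CIs overlap | 100% | 100% | 100% |
| Significance of trial result changes | 0.6% to 10.7% | 10% to 29% | 26% to 59% |
| Paired CI excludes zero | 4% to 6% | at least 99.9% | 100% (N = 280) |

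Overlap does not distinguish a swap that moves the result from one that does not. A change of significance does respond to a shift. It also occurs by chance without one, most often when a confidence limit lies near zero.

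**The case against.** The strongest reply is that the stated target is the effect on the trial's conclusions and that the project is declared exploratory and descriptive. For the question of whether EMO would have concluded differently, running its own code on both scores and showing both results is a direct and legitimate answer. That stands, and it is why the display should be kept. It does not remove the gap: the remedy is an estimate with an interval, not a test, and the protocol itself promises intervals where appropriate.

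A reader might infer that the planned analysis is bound to show no impact. The protocol does not support this. It sets no overlap rule, and read by change of significance the display can show an impact. A reader might also infer that the impact is never estimated, or that a shift of, say, 0.3 points would be hidden. That also goes too far: both means are reported, and subtracting them gives the point estimate. Nor would the paired interval always settle a 0.3-point shift, since at item correlation 0.5 its half-width can reach 0.36.

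Finally, bootstrap details and complete-case rules could sit in an analysis plan that is not shown. That is fair as to detail. The point here concerns the output that the protocol does fix, which a small addition would improve.

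**Conclusion.** The point holds in a limited form. Objective 2 shows both estimates, but their separate intervals give no uncertainty for the change caused by the swap, and the protocol names no size of change that would matter. That the intervals are paired and that the six shared items cancel follows from the protocol alone. The gain in precision, roughly 4 to 11 times, rests on assumed SDs, item correlations, allocation and N, and would be smaller after baseline adjustment. Nothing in the documents shows that the arms do differ in how the two items are answered, or what shift on the 0 to 28 scale is important. This is a worthwhile, low-cost improvement to a descriptive analysis, not an error that invalidates it.

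**What to change.** Keep the two between-group estimates with their CIs as description. Add the difference between them (modified minus original) with a 95% CI, on participants who have both scores at the time points the model uses. Obtain it in one of two ways:
- a participant-level paired bootstrap of the EMO model, with both versions fitted to each resample; or
- unadjusted, the between-arm difference in mean (RECAP itch − POEM itch) at week 8.

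Interpret the interval in POEM points, if possible against a size of change stated before the analysis. The protocol offers no figure to anchor that size, so the team would have to choose and justify one. Add a sentence that overlap of the two separate CIs will not be read as evidence of no impact.

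The cost is a few lines of code and one extra row in the results table. Both week-8 itch items are in the codebook (poem_a_18 and recap_a_28). The variable list under Data sources names only baseline RECAP questions, so it should be extended to the week-8 itch item, which Objective 2 needs in any case.

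### No planned analysis estimates the size or direction of a systematic RECAP-minus-POEM difference in the itch-frequency item, although research question 1 is about interchangeability

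*Protocol*

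**What the plan says.** All references are to the Protocol, Methods.

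- **Research question 1** asks whether the two itch-frequency items are "sufficiently similar to enable collection only once".
- **Objective 1**: agreement "will be evaluated using both a weighted kappa (primary method) and kappa". The item is scored 0 to 4. The weights are listed, for example "Difference of 1 between the POEM and RECAP questions = 0.89". The text that follows sets 0.8 or more as the level suggesting that the item may not need asking twice.
- **Objective 2**: "The trial results will be re-calculated using the total POEM scores at baseline and week 8", once with the original score and once "Using 6 items from the original POEM score, plus the frequency of itch question from the RECAP outcome instrument". The model is not shown; "the original syntax from the trial analysis will be used". One output is named: "Trial results will be presented with mean between group difference and 95% CIs to explore the likely impact on the trial conclusions".
- **Objective 3** uses Pearson's correlation with a 95% CI and the same 0.8 threshold.
- **Data sources** restricts kappa and correlation to baseline.

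Analysis methods adds that the work is exploratory and mainly descriptive. It names no paired item difference, no comparison of marginal distributions and no within-arm comparison of the two scorings.

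**The concern.** The items are near-identical in wording and differ in the questionnaire around them. The natural question is whether that context moves the answer. If people tend to answer lower in one questionnaire, substituting one item for the other moves individual POEM totals and arm means, and makes them less comparable with trials that scored POEM from its own item.

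The between-group difference is not built to show this, and neither r nor kappa gives a size or direction. A moderate one-way shift could therefore meet the 0.8 rule and leave Objective 2 unchanged, and research question 1 would be answered yes without the shift being reported. The results are meant to inform HOME consensus recommendations, so the answer will be used beyond this dataset.

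**Working it through.** The protocol gives no figure to reproduce and no item distributions. The distributions and shares below are assumptions.

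**1. Objective 2.** Let d = RECAP item minus POEM item. The other six items are common to both scorings, so modified total minus original total = d. The raw between-group difference changes by

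mean(d | arm X) − mean(d | arm Y).

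If d has the same mean in both arms, this is 0. In a baseline-adjusted model, constant shifts at baseline and week 8 go into the intercept.

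A floor at 0 makes the shift not quite constant, so this was also simulated (n = 281, baseline-adjusted model, 400 runs per row, treatment effect assumed):

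| Share one category lower | Mean item shift | Difference, original | Difference, re-scored |
|---|---|---|---|
| 30% | -0.26 | -0.885 | -0.875 |
| 50% | -0.435 | -0.859 | -0.849 |
| 100% | -0.864 | -0.889 | -0.861 |

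The contrast moves by 0.01 to 0.03 points.

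**2. Kappa cannot separate shift from noise.** Take POEM answers uniform over 0 to 4 (20% each) and use the listed weights 1, 0.89, 0.56, 0.

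- *One-way:* half answer RECAP one category lower and those at 0 stay. Exact agreement = 0.2 + 0.8 × 0.5 = 0.60. Observed weighted agreement = 0.60 + 0.40 × 0.89 = 0.956. The RECAP margins are 0.3, 0.2, 0.2, 0.2, 0.1. The column sums of the weights are 2.45, 3.34, 3.90, 3.34, 2.45. Expected agreement = 0.2 × (0.735 + 0.668 + 0.780 + 0.668 + 0.245) = 0.6192. Kappa = (0.956 − 0.6192)/(1 − 0.6192) = 0.884. Mean shift = −0.8 × 0.5 = −0.40.
- *Balanced:* a quarter lower and a quarter higher, staying put at the ends. Exact agreement is again 0.60. The margins stay uniform, so expected agreement = 0.04 × 15.48 = 0.6192 and kappa = 0.884. Mean shift = 0.

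Unweighted kappa is (0.60 − 0.20)/0.80 = 0.50 in both. The two kappas are identical, yet one pattern is systematic and the other is not.

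**3. How large a shift passes the 0.8 rule.** One-way shifts, listed weights. Percentages for categories 0 to 4: uniform 20 each; moderate 5/20/25/20/30; ceiling-heavy 3/12/15/20/50.

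| Distribution | Share lower | Mean shift | Weighted kappa | Unweighted kappa | r |
|---|---|---|---|---|---|
| Uniform | 50% | -0.40 | 0.884 | 0.50 | 0.938 |
| Moderate | 50% | -0.48 | 0.847 | 0.40 | 0.923 |
| Ceiling-heavy | 50% | -0.49 | 0.829 | 0.36 | 0.917 |
| Uniform | 70% | -0.56 | 0.838 | 0.30 | 0.937 |
| Moderate | 70% | -0.66 | 0.791 | 0.18 | 0.929 |
| Ceiling-heavy | 70% | -0.68 | 0.769 | 0.15 | 0.925 |
| Uniform | 100% | -0.80 | 0.769 | 0.00 | 0.970 |
| Moderate | 100% | -0.95 | 0.712 | -0.15 | 0.986 |
| Ceiling-heavy | 100% | -0.97 | 0.685 | -0.15 | 0.991 |

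The listed weights equal 1 − (difference/3)², the quadratic form for four categories. With the five-category form the 50% rows give 0.85 to 0.90, so the reading is the same.

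**4. Precision of the missing estimate.** With 296 − 15 = 281 pairs (assuming the 296 includes the 15 excluded parent-completed records, with no missing items) and d = −1 in 40%: SD = √(0.4 × 0.6) = 0.490, SE = 0.490/√281 = 0.029, 95% CI about ±0.06. With 200 pairs: SE = 0.490/√200 = 0.035, about ±0.07.

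**The case against.** **Objective 2 answers the question it poses.** It asks about impact on the trial's results, and a two-arm trial concludes from a between-group difference. If a shared shift leaves that unchanged, reporting no impact on the conclusion is correct. This stands. A reader might infer that Objective 2 is mis-specified or would produce a false result. The documents do not support that, and nothing in them says Objective 2 alone settles research question 1.

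**Kappa reacts to a shift.** This stands too. Unweighted kappa is planned, and 0.36 to 0.50 would be visible. Weighted kappa fails 0.8 once 70% to 100% shift, depending on the distribution. A reader might infer that any systematic difference would pass unnoticed. It would not: a large one would appear as poor agreement, though not as bias.

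**The shift may not be common to both arms.** The Variable Codebook has arm X completing POEM weekly and arm Y only at baseline and week 8, so d could differ by arm at week 8. Objective 2 would pick that up. The cancellation applies only to the shared part.

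**The scenario is assumed and the effect small.** The documents give no evidence that a shift exists, and 0.4 to 0.5 points is 1.4% to 1.8% of a 28-point range. They give no important-difference value against which to judge it. That limits the weight of the point but does not remove the gap.

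**The detail could sit elsewhere.** Descriptive tables, the 5x5 margins or the unseen trial syntax may reveal the shift. But this protocol itself fixes the statistics for each objective and the collect-once threshold, and it commits to none of these outputs.

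**Conclusion.** The point holds in a limited form, as a low-cost improvement and not as an error in Objective 2. Research question 1 concerns interchangeability, and no named analysis estimates the size or direction of a systematic difference between the two items. The exposed range is one-way shifts of up to about half a category. Such shifts meet the primary 0.8 criterion (read as applying to weighted kappa) and leave the between-group difference essentially unchanged.

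The cancellation is algebraic and needs only a shift common to both arms. The kappa and correlation values rest on the assumed item distributions and on one-category, one-way movement. Whether any shift is present in the EMO data cannot be told from the protocol.

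**What to change.** - **Objective 1:** beside kappa, report the baseline paired mean difference (RECAP item minus POEM item) with a 95% CI, and the 5x5 cross-tabulation.
- **Objective 2:** at baseline and week 8, report arm means under both scorings and the mean change in POEM total (modified minus original) with a paired 95% CI.
- **Interpretation:** state that an unchanged between-group difference shows only that the item difference does not depend on arm, and that the collect-once conclusion will consider the mean shift as well as weighted kappa.

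Limits of agreement are optional; they are coarse for a difference driven by one five-level item.

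The cost is a few lines of Stata on data already held, one extra table and one or two sentences. If a small shift is found, the collect-once message will need qualifying.
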